Precautions are in place to ensure the data is secure by using passwords and encryption, because the research involves web-based surveys.

Audio and/or video recordings will be transcribed and then destroyed to eliminate audible identification of subjects.

Other (specify):

5. Protected Health Information

Five types of protected health information will be collected, subject's name, telephone number, email address, medical record number, and date of birth. The first three are required to allow for the 3- and 6-month follow up, and the medical record number will enable us to extract data on post-operative pain and opioid use. Date of birth will be collected to verify age. These data will not be shared with persons not involved in the study, all of whom have completed HIPAA training.

6. Compensation:

Subjects will receive no compensation for participating in the study.

7. Data and Safety Monitoring:

The Penn Center for Substance Abuse Treatment (CSA) has a standing data and safety monitoring board (DSMB) which will be used for this study. The purpose of the DSMB and consistent with NIH guidelines is to

assure that the safety of subjects is protected while scientific goals are being met. Specifically, the CSA DSMB is charged with monitoring the safety of participants and the quality of data, as well as the appropriate termination of studies when significant benefits or risks have been uncovered or when it appears that a clinical trial cannot be concluded successfully.

All board members meet NIH requirements regarding background and experience, and none will have ethical conflicts including financial interest related to study outcome. Individuals invited to serve on the board disclose any potential conflicts in writing. The board meets every six months (unless more frequent meetings are deemed necessary) and is chaired by [name] Ph.D. a faculty member within the Department of Psychiatry at the University of Pennsylvania. Other members of the board include [name]. (senior statistician), [name]., [name], MSN, CRNP who are faculty members or staff of the Perelman School of Medicine at Penn. Issues related to recruitment, safety and efficacy, whether the study questions are being answered, conflict of interest, confidentiality, and ongoing study review (including AEs, SAEs, and regulatory issues) are assessed.

Following each DSMB meeting, the designated member standing in for the Chair will make recommendations to Drs. [name] and [name] and a final report (edited by all Board members not in conflict with this project) will be prepared and submitted to NINR, the Penn IRB, and the FDA (if required) according to each body's reporting requirements. In addition, a Data Safety Monitoring Board report is issued to the NINR Project Officer with the annual progress report.

The DSMB will meet to review safety data every six months (unless more frequent meetings are deemed necessary). At least two weeks prior to each meeting, the investigative team will submit to the DSMB a DSMB Report detailing screening activities; reasons for screening failures; subject enrollment (actual vs. expected); sociodemographic characteristics of enrolled subjects; and subject disposition (including reasons for attrition). In addition, the number and nature (severity and relatedness to study procedures) of all adverse events will be described. Finally, a random or purposive sample (depending on DSMB request) of subject case report forms (CRFs) will be submitted with the DSMB Report, to enable assessment of compliance with IRB requirements, conformance with informed consent requirements, verification of source documents and investigator compliance.

In the event that a subject scores high on the depression scale, a licensed clinical psychologist (co-PI [name]) will be available to assess immediately any patient who exhibits extreme anxiety, depression or suicidal ideation on routine screening or during the preoperative period. All research and clinical staff will call his cell phone when a patient with significant anxiety, depression or suicidal ideation is encountered. All patients who acknowledge extreme anxiety, depression or suicidal ideation and intent will be contacted immediately by [name] and an appropriate treatment plan will be enacted.

8. Investigator's Risk/Benefit Assessment:

Based on the characteristics of the risks associated with study participation, and efforts in place to minimize these risks, the risks to subjects are considered reasonable in relation to the anticipated benefits to research participants and others.

INFORMED CONSENT:

1. Consent Process:

Informed consent will be obtained from patients who express interest participating in the study by the trained study coordinator who has experience in obtaining consent from research subjects. It will be obtained in a private office at time that is convenient for the prospective subject. Specifically, the study coordinator will read out loud in English the consent form to the patient, stopping at regular intervals to assess the patient's level of understanding of the information in the consent form, clarifying content, and answering questions. Patients will be told that they need not sign the consent at this time, and that they may take it home to review for as long as they would like prior to deciding to provide informed consent. Patients will be assured that if they choose not to participate, it will have no effect on the medical care they receive or any other social retributions. Any evidence of mental impairment will be evaluated by the study coordinator via informal assessment; if impairment is suspected, the consent process will be halted, and either co-PI [name] or [name] will be called upon to further evaluate.

2. Waiver of Informed Consent:

Not applicable.

RESOURCES NECESSARY FOR HUMAN RESEARCH PROTECTION:

The percent effort and qualifications of the members of the investigative team are more than adequate to conduct the research. Specifically, co-principal investigator, [name] [name] will contribute 1.44 calendar months effort for the duration of the project and take primary responsibility for the development and pilot testing of the cognitive behavioral therapy (CBT) intervention, working closely with consultants [name] and [name]. He will be responsible for training and monitoring the study coordinator/coach to effectively deliver the opioid tapering motivational interviewing (MI) component of the intervention and monitoring the fidelity of this delivery. He will serve as the CBT expert during the efficacy testing of the intervention and troubleshoot any issues that arise as participants undergo the 4-week training. In addition, he will take the lead in directing and interpreting the CBT feasibility and efficacy data in data analysis and dissemination activities and play a primary role in writing reports of the findings and subsequent grant applications.

Co-principal investigator, [name], PhD, will contribute 1.44 calendar months effort to the project over the two-year project duration. She will be responsible for obtaining IRB approval, directing development of the REDCap database, and overall coordination of the efficacy testing of the intervention. Working closely with Co-I [name], she will monitor subject recruitment and enrollment efforts and verify subject eligibility. She will also oversee the day-to-day activities and performance of the Study Coordinator, and be responsible for monitoring the accuracy, quality and completeness of data collection, ensure protocol fidelity, and compliance with all regulatory and funding agencies. She will direct data analysis, and play a primary role in dissemination of findings and grant writing.

The Co-investigator, [name] will contribute 0.6 calendar months during both years of the project. He will be responsible for working closely with Study Surgeons [name] and [name] to identify and recruit potentially eligible patients for study enrollment. He will work with the Study Coordinator to establish eligibility and obtain informed consent. Importantly, he will serve as the primary liaison to the orthopedic surgeons and the surgery service to ensure effective collaboration as a means to achieve study objectives. In addition, he will assist with data interpretation and the dissemination of findings. [name] will serve the primary study clinician, managing any health-related issues experienced by study subjects during study participation.

Statistician, [name], will contribute .45 calendar months effort to the project during Year 2 only. He will serve as the study statistician, working with the REDCap derived database to the complete the analysis as outlined in the Research Plan. Specifically, he will oversee data cleaning and variable construction, run interim analysis, and complete the descriptive and multivariate analysis required to meet the study specific aims. As results become available, he will work closely with the Co-PIs to refine the analytical plan as needed and contribute to the writing of dissemination materials.

The Study Coordinator/Coach, TBH, will devote 12 calendar months effort to the study over both years of the project. This individual will come to the project with experience in coordinating human subject clinical research studies and be responsible for enrolling subjects, scheduling study visits, all aspects of data collection, entering study data into REDCap, and engaging in ongoing communication with IRB, study setting and U Penn School of Medicine and Nursing, Department of Anesthesiology and Department of Orthopaedic Surgery. In addition, this individual will receive directed training and monitoring from Co-PI [name] to oversee delivery of the CBT and opioid tapering MI intervention. In this role, this individual will serve as a "coach" to the subjects, contacting them on a weekly basis prior to surgery, educating and motivating them to engage in preoperative opioid reduction.

Participants will be recruited from the nationally renowned Department of Orthopaedic Surgery at PPMC. Center surgeons perform approximately 1800 major TKAs per year, an estimated 20-30% of whom have been taking opioids for at least 3 months for the treatment of a chronic nonmalignant pain condition, resulting in a recruitment pool of 30 to 45 patients per month, providing an adequate source of the necessary 12-13 enrollments per month.

In addition, the facilities and resources are adequate to safely conduct the study. Situated within the Department of Psychiatry is the Center for Studies on Addiction (CSA), where Co-Principal Investigator [name] holds an appointment. A primary mission of the CSA is to continue to advance the cutting edge of knowledge on the nature of addiction and the best ways to treat this disorder. The CSA has, for the past 40 years, been an important

national and international resource for addictions research. The PI ([name]) has conducted large-scale studies on pain and opioid use disorders and suicide and has an established relationship at the primary recruitment site.

The CSA is housed in 16,400 sq. ft. of space in a building near the UPenn campus located adjacent to the primary recruitment site, PPMC. [name] has a locked private office space ([name], approximately 400 square feet). All faculty offices come equipped with locked filing cabinets, bookshelves, desk, minimum 4 GHz computer with HP printer, Windows XP service pack 3 operating system, Microsoft Office Professional (Word, Excel, PowerPoint, Access), SPSS or SAS statistical analysis software, and e-mail and internet access. Copier, printer, fax and scanner facilities are available in the center. In addition, the CSA has several meeting rooms with teleconferencing capabilities,

Co-Principal Investigator [name] and Biostatistician [name] benefit from the extensive research resources at the University of Pennsylvania School of Nursing, which boasts the highest rate of NIH funding across nursing schools in the country. The School of Nursing has outstanding facilities and resources to accomplish its mission of excellence in research. Specifically, the *Office of Nursing Research (ONR)* support faculty and students in applying for, obtaining, and managing funding for scientific research projects. The ONR delivers a suite of services throughout the lifespan of a research grant - from conception to closeout. The ONR also provides highly skilled statistical support, hosts an expertly staffed state-of-the-art nursing research laboratory, conducts mock reviews, offers guidance with IRB protocol submission and regulatory compliance, and provides editing services for scientific and English content of proposals. The ONR also provides various learning opportunities for faculty, staff and students through weekly colloquia and six face-to-face Responsible Conduct of Research seminars a year. Colloquia are presented by Penn Nursing faculty and guest lecturers from complementary disciplines to foster multidisciplinary research collaborations and initiatives.

For implementation of the proposed project, School of Nursing facilities include adequate computer, statistical support, and office resources necessary to undertake and complete the proposed research project successfully. Specifically, a wide range of computing resources is available at the University of Pennsylvania. Support for these resources is divided among a number of organizations. The broadest organization is led by the Vice Provost for Information Systems and Computing (ISC), which supports PennNet, the campus-wide network, providing both intra-campus communication, and access to the Internet. ISC manages the Data Warehouse, the University's central repository for administrative data, and oversees the development and maintenance of most of the administrative systems at Penn. Administrative systems are those used by all centers and the 12 schools in support of academic, business/financial, and research administration. ISC also provides a number of other campus-wide services, including development of technology training programs, evaluation of universally-used software (e.g., email, anti-virus packages, communications software), and management of software site licenses. ISC provides leadership on a number of technology issues, such as security and privacy.

Computing support is also available from the Office of Technology and Information Systems (OTIS) unit in the School of Nursing. OTIS supports a school-wide local area network, provides desktop support, offers routine training services, maintains liaison with technology representatives in each department, and runs two computer laboratories. The larger of these laboratories, containing 21 personal computers, is available to all members of the School of Nursing. The second laboratory, the Doctoral Computer Laboratory, is exclusively for the use of pre- and post-doctoral trainees. This lab is equipped with 8 personal computers with software resources including SAS, SPSS, STATA, ATLAS.

OTIS provides access for researchers to REDCap and to store data on a secure research server, which is backed up nightly, with weekly backups stored off site. The server is behind a firewall and is registered as a "Critical Host" by the University. This means OTIS follows all University policies regarding critical hosts: firewalls, access controls, timely patch management and anti-viral scans and software updates, and an enterprise system monitoring solution (allowing us to detect and address intrusion attempts). In the future, we will be enhancing the research server with the following: folder-based intrusion detection, encryption, and an off-site mirroring solution.

With respect to statistical support, the Office of Nursing Research (ONR) provides a team of highly skilled doctoral and master's level statisticians through the BECCA (Biostatistics * Evaluation * Collaboration * Consultation * Analysis) Lab, along with Penn Nursing research assistants and biostatistics graduate interns, who work with investigators to design, implement, analyze, and disseminate their research. Collaboration with a fully-supported, skilled statistician typically yields clearly articulated results that meet grant reviewers' expectations and peer-review. Statistical collaboration provides support in the areas of sample size, power analysis computation, data

management, statistical analysis, and results presentation. Expert at identifying and addressing potential issues, BECCA statisticians may suggest exploring alternatives such as more appropriate statistical designs, or perhaps modern modeling techniques. BECCA statisticians not only ensure statistical rigor and appropriateness, but also make sure that a study design is practical, feasible, and scientifically justifiable. The BECCA Lab is directed by and houses study biostatistician, [name].

Because the PAINTrainer intervention is web-based, and can be accessed from a computer, tablet or smartphone, dedicated university computer resources are not necessary for the proposed work; written into the budget is the purchase of four(4) ipads with internet connectivity to provide subjects who do not have a suitable device.

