COVER PAGE

Pre-op Cognitive Behavior Therapy to Decrease Chronic Post-Surgical Pain in TKA

NCT04814992

November 23, 2020

PRINCIPAL INVESTIGATORS: [name] & [name], PhD, FAAN

PROTOCOL TITLE: Pre-op CBT to Reduce the Risk for Development of Chronic Post-surgical Pain in Patients undergoing Total Knee Arthroplasty

INTRODUCTION AND PURPOSE:

A significant number of patients develop chronic post-surgical pain following knee joint replacement surgery, and the risk factors for this problematic outcome have been identified. Proposed is the development and preliminary efficacy testing of a novel computer-assisted cognitive behavioral intervention integrating opioid taper delivered in the four weeks prior to surgery to address these risk factors, with the expectation that both the severity of post-operative pain and the subsequent incidence of chronic post-surgical pain will be reduced. In that chronic post-surgical pain brings with it diminished functionality and quality of life, ongoing opioid use, and direct patient costs, it is critical that interventions aimed at mitigating its development are implemented and evaluated in the clinical setting.

OBJECTIVES:

In a sample of adult men and women with chronic pain, on opioid therapy and undergoing a planned TKA, the objectives of this randomized clinical trial are to:

1. Add a motivational interviewing component to a validated computer-assisted CBT intervention for chronic pain (PAINTrainer) to encourage opioid tapering in the 4 weeks prior to surgery.
2. Describe the efficacy of the 4-week targeted pre-operative CBT intervention in 75 TKA patients to decrease preoperative chronic pain severity, preoperative opioid consumption, and symptoms of depression, anxiety and pain catastrophizing prior to surgery in comparison to 75 TKA patients randomized to treatment-as-usual.
3. Describe the effects of a 4-week targeted pre-operative CBT intervention in 75 TKA patients on 72hr post-operative pain severity, and 3- and 6-month rates of CPSP in comparison to 75 TKA patients randomized to treatment-as-usual.

BACKGROUND:

Knee Joint Replacement and Chronic Post-surgical Pain

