A power analysis was conducted for the post-operative pain outcomes; being a novel intervention, opioid taper outcomes were not considered. Estimated group means, variances, and effect-size were drawn from the literature.^{41,42} The sample size estimate was derived for the primary outcome variable, chronic pain severity, using an expected baseline mean of 4.82 (Effect size: 0.33). Based on estimates obtained, a sample size of 75 participants provides 80% power to detect a pre-post improvement in pain severity (14.5%), depression (21.3%), anxiety (24.3%), and catastrophizing (29.5%), statistically significant at alpha of 0.05. Being a novel intervention, the analysis for chronic post-surgical pain will be considered exploratory and used to obtain effect size estimates. We anticipate a low attrition rate (10%) and will over-recruit 16 additional participants (total 83 subjects per group) to retain adequate power.

2. Key Inclusion Criteria:

[figure not shown]

Figure 1. Predictive factors of CPSP following TKA

1. Males and females, age > 21 years
2. Chronic non-malignant pain of at least 3 months duration
3. Morphine equivalent daily dose (MEDD) > 50 milligrams for at least 3 months
4. Able to enroll at least 4 weeks prior to planned surgery
5. Able to speak, read and comprehend in English at the 6th grade or higher proficiency

Participants will be selected so as to represent the gender, ethnicity, and age of the patient population of individuals seeking TKA in greater Philadelphia area, thus the sample is expected to be 50% women, 55% white, 35% African-American, 6-8% Latino, and 2-4% other or multiracial, and on average 67 years of age. No restrictions on gender or ethnicity will be applied. Because total knee arthroplasty surgery is uncommon in children, individuals under the age of 21 will not be included in this proposed study.

3. Key Exclusion Criteria:

1. Pain of malignant origin
2. Current or past history of opioid use disorder (including those on medication-assisted therapy)
3. Revision of TKA
4. Comorbid CNS disease such as dementia, HIV, psychosis, poorly controlled bipolar disorder or any condition interfering with informed consent

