For the second study objective, we expect that participants, who receive a MI intervention along with a validated computer-assisted CBT intervention for chronic pain (PAINTrainer) will demonstrate a significantly greater improvement in outcome variables from baseline vs those receiving usual care. The outcome variables will include change in the severity of pre-operative chronic pain, opioid use, and psychological risk factors (depression, anxiety, catastrophizing) for CPSP in the 4 weeks prior to surgery. Specifically, a mixed model analysis will be fit to the data using the Proc Mixed procedure in SAS.^{56,57} Residual modeling will be performed to check for significant violations in the distribution and constant variance assumptions and determine if variance stabilizing or normalizing transformations should be applied. Furthermore, sensitivity analyses will be run considering dichotomous versions of the outcome variables using multiple logistic regression.

For the third study objective, we will describe the effects of the CBT intervention on 72hr post-operative pain severity, and 3- and 6-month rates of CPSP in comparison to patients who received treatment-as-usual. A mixed effects model will be fit with Treatment Group (intervention and usual care) as a between subject factor and Time (72hr, month 3 and 6) as a categorical within-subjects factor. We will include as baseline covariates any factors that differ significantly between the groups at baseline or show significant relationships with the outcome.

Potential confounders (medical comorbidities, post-operative complications) will also be considered in the analysis.

The results from the mixed model analyses will be summarized by mean (SE) change from baseline for each group at each time point. The primary hypothesis will be evaluated at the alpha = 0.05 level and all contrasts/hypotheses will be considered exploratory and results will be interpreted with caution at alpha equal to 0.05 level. The primary goal will be to obtain reliable effect size estimates to inform larger studies. In that women are more likely to develop CPSP than men,^{8,16} sex as a biological variable will be considered as a possible moderator in all analyses.

RISK/BENEFIT ASSESSMENT:

1. Risks:

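### The stated 80% power is for a pre-post improvement; no power is stated for the randomized comparison with usual care that objective 2 tests

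*Combined protocol and SAP*

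**What the plan says.** Power is stated in one place, under Characteristics of the Study Population, 1. Target Population and Accrual. The paragraph opens with "A power analysis was conducted for the post-operative pain outcomes". It then sizes the study on chronic pain severity, "using an expected baseline mean of 4.82 (Effect size: 0.33"), and says that "a sample size of 75 participants provides 80% power to detect a pre-post improvement in pain severity (14.5"%). Corresponding percentages follow for depression (21.3%), anxiety (24.3%) and catastrophizing (29.5%), all at alpha 0.05. On the source of the inputs it says only "Estimated group means, variances, and effect-size were drawn from the literature". For attrition, the study "will over-recruit 16 additional participants (total 83 subjects per group) to retain adequate power".

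The hypothesis is worded differently. Under Study Procedures, 5. Statistical Analysis, patients given the intervention "will demonstrate a significantly greater improvement in outcome variables from baseline vs those receiving usual care". Objectives, item 2 likewise sets 75 intervention patients against 75 controls: "Describe the efficacy of the 4-week targeted pre-operative CBT intervention in 75 TKA patients", with outcomes including "symptoms of depression, anxiety and pain catastrophizing prior to surgery in comparison to 75 TKA patients randomized to treatment-as-usual".

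The statistical section tests a primary hypothesis at 0.05. It also treats contrasts as exploratory and names effect-size estimation as the main goal. The rationale for the exclusion criteria calls the study a small pilot.

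**The concern.** A pre-post improvement is a change within one arm. The objective 2 hypothesis is a difference between arms in that change. For the same standardized effect and the same number per arm, the second is harder to detect, because the control arm adds its own sampling error and any improvement under usual care is subtracted. The power that justifies 75 per group, and enrolment of 83 per group to protect it, may therefore belong to a contrast other than the one randomization was set up to test.

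A reader who takes the 80% as the power of the trial could misread a non-significant group difference as fairly strong evidence of no effect. The team would also have no stated precision against which to judge the effect-size estimates that are its declared goal.

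**Working it through.** **Inputs from the plan.** Effect size 0.33; 75 participants, 75 per arm; alpha 0.05; baseline mean 4.82; improvement 14.5%, which is 0.145 × 4.82 = 0.70 points.

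**Not in the plan, so assumed.** Two-sided test; the SD unit of 0.33 (SD of change, or cross-sectional SD); r = 0.3, 0.5 or 0.7, with equal SDs at baseline and T0; the change under usual care. All power figures use the noncentral t distribution.

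**1. The plan's own figure.** Paired t-test in one arm, noncentrality 0.33 × √75 = 2.86, 74 df: power **80.5%** (80.0% with 74 patients). With 0.33 in change-SD units, no further input is needed. In cross-sectional SD units the one-arm test gives 66%, 80.5% and 95% at r = 0.3, 0.5 and 0.7, so it matches the stated figure only at r = 0.5.

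**2. The same 0.33 between arms.** Two-sample t-test on change scores in change-SD units, noncentrality 0.33 × √(75/2) = 2.02, 148 df: power **52%**. The difference detectable with 80% power is 0.46 change-SD, and the 95% CI half-width is t × √(2/75) = 0.32 change-SD.

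**3. Other units and baseline adjustment.** Here the whole 0.33 is taken as the group difference: either no change under usual care, or 0.33 already net of it. Effective d:

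- change-SD units, adjusted: 0.33 × √(2(1−r)) / √(1−r²) = 0.409, 0.381, 0.358
- cross-sectional SD, change scores: 0.33 / √(2(1−r)) = 0.279, 0.330, 0.426
- cross-sectional SD, adjusted: 0.33 / √(1−r²) = 0.346, 0.381, 0.462

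| Power, 75 per arm | r = 0.3 | r = 0.5 | r = 0.7 |
|---|---|---|---|
| Change-SD, change scores | 52% | 52% | 52% |
| Change-SD, adjusted | 70% | 64% | 59% |
| Cross-sectional SD, change scores | 40% | 52% | 74% |
| Cross-sectional SD, adjusted | 56% | 64% | 80% |

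In cross-sectional SD units, 80% is reached at r of about 0.70 with adjustment, or 0.74 with change scores.

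**4. Change under usual care.** Suppose instead that 0.33 is the intervention arm's own 14.5% change, and that controls move by 3% of baseline (both assumptions).

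- Controls improve: d = 0.33 × 11.5/14.5 = 0.262
- Controls worsen: d = 0.33 × 17.5/14.5 = 0.398

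Adjusted power at r = 0.5 is then 45% or 80%. Over all cells of the table the range is **27%** (controls improve; cross-sectional SD, change scores, r = 0.3) to **92%** (controls worsen; cross-sectional SD, adjusted, r = 0.7).

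**5. Detectable difference and precision, adjusted analysis.** Multiply the unadjusted 0.46 and 0.32 by √(1−r²) / √(2(1−r)) for change-SD units, or by √(1−r²) for cross-sectional SD units.

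| 75 per arm, adjusted | r = 0.3 | r = 0.5 | r = 0.7 |
|---|---|---|---|
| d for 80% power, change-SD | 0.37 | 0.40 | 0.42 |
| 95% CI half-width, change-SD | 0.26 | 0.28 | 0.30 |
| d for 80% power, cross-sectional SD | 0.44 | 0.40 | 0.33 |
| 95% CI half-width, cross-sectional SD | 0.31 | 0.28 | 0.23 |

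**The case against.** The strongest reply is that the within-arm reading is an inference. The paragraph speaks of group means and counts subjects per group, which suits a two-group calculation. The Background describes the programme's earlier results against an education control, so 0.33 may already be a net effect. Pre-post improvement could be shorthand for change from baseline, and a between-group route to 80% exists at r near 0.70. This stands: an unreported between-group calculation cannot be excluded. It does not close the gap, because that route needs a correlation and an SD unit that appear nowhere in the plan.

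The pilot and estimation framing also stands, and it lowers the severity. It does not remove the point, since a primary hypothesis is still tested at 0.05, over-recruitment is justified by power, and no precision is given for the estimates. The Study Design section does plan within-subject as well as between-group comparisons, so a within-arm power has some use; it is not the power of the randomized comparison.

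A reader might go further and infer that the trial is shown to be underpowered, that its power lies between 40% and 80%, or that the 80% is miscalculated. The documents support none of these. The figure is right for a paired test. The 40% to 80% range holds only for r of 0.3 to 0.7 with the whole 0.33 as the group difference. The inputs that would settle the true power are not given.

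Nor do the documents prove that the words post-operative are the slip in the opening sentence. The two time points of pre-post are never named, and the same scales are scheduled again at 3 and 6 months. The pre-operative outcomes of objective 2 are the likelier target.

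**Conclusion.** The point holds as a mismatch between the stated power and the hypothesis tested; it is not an arithmetic error. The only stated power reproduces as a one-arm paired test, and that is the simplest match, not a proven one. The power of the randomized comparison is unstated and cannot be derived from the plan. The figure nearest to a like-for-like reading is 52%, which assumes change-SD units, no adjustment and the whole 0.33 as the group difference. The ranges around it are illustrations and do not bound the true value. Confidence is high that the contrast and its inputs are missing. Severity is low to moderate: worth correcting, because the enrolment target is justified by power, but not a threat to a study whose main aim is estimation.

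**What to change.** Keep the sample size and make these changes to the text:

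1. Say which contrast the 80% refers to. Unless a between-group calculation can be shown with its inputs, label it as within-arm and do not present it as the power of the randomized comparison.
2. Adjust the primary group comparison of T0 BPI for the baseline BPI, which is already collected.
3. State power, detectable difference and 95% CI half-width for that adjusted analysis at 75 per arm, together with the SD unit of 0.33, the assumed correlation and the assumed change under usual care. The tables above give the values for r of 0.3 to 0.7.
4. Put the depression, anxiety and catastrophizing figures on the same basis once their inputs are given.
5. Reconcile the opening reference to post-operative pain outcomes with the pre-operative outcomes that the paragraph appears to power.

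The cost is protocol wording and a commitment to baseline adjustment; no patients, visits or data are added. The downside is that the stated power becomes less favourable under most assumptions, and the team must commit to an SD unit and a correlation.
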